15.1.3 Endpoints

Safety and tolerability will be the primary endpoint and it will be monitored during the course of the study as specified below:

Safety and Tolerability Parameters

- Vital signs: systolic (SBP) and diastolic (DBP) blood pressure, heart rate, and body temperature.
- ECG (12-lead ECG)
- Safety laboratory tests: haematology, coagulation, plasma biochemistry.
- Presence of anti-LR12 antibodies
- Adverse events: from screening until study completion.

Secondary endpoints include the following:

Pharmacokinetics

Plasma concentrations of LR12 will be measured by a validated LC-MS/MS assay and analysed using non-compartmental methods to obtain estimates of the PK parameters.

Pharmacodynamics (exploratory)

The concentration profiles of biomarkers (sTREM-1, immune and vascular related biomarkers) over time and biomarker mRNA levels will be analysed.

Clinical Parameters

- Resolution of organ dysfunction (SOFA score total and individual domains)
- Vasopressor use
- Invasive mechanical ventilation
- Renal support
- Time until shock reversal defined as cessation of vasopressor support for 24 hours
- Mortality at day 28 and day 90

Safety and tolerability will be the primary endpoint and in addition, the exposure of MOTREM will be analysed. The biomarker concentration profiles over time and the area under the concentration (AUC) curves will be analysed as secondary PD variables.

The MOTREM concentration profile over time and the main derived PK parameters will be analysed as PK endpoints.

The endpoints and their analysis will be further specified in the statistical analysis plan (SAP).

15.1.4 Baseline Characteristics and Patient Disposition

Baseline characteristics (medical history, previous therapies, APACHE II Score, physical examination and serum pregnancy test), demographics and disposition data will be summarised by treatment group (Placebo, Dose level 1, Dose level 2 and Dose level 3).

15.1.5 Safety Analyses

Adverse events will be coded using the MedDRA dictionary version 18.1 or higher. Treatment emergent adverse events (events start after the first dose of investigational treatment or events present prior the administration of investigational treatment and worsened during the study (increased in severity)) will be classified by primary system organ class, preferred term and treatment group. Separate summaries will be performed for study medication related events, death, serious adverse events, adverse events leading to discontinuation of study medication and other adverse events of interest.

Other safety parameters that will be assessed include safety laboratory parameters (haematology, coagulation, biochemistry, arterial blood gases etc), vital signs (SBP, DBP, heart rate and body temperature), ECG and exposure of MOTREM. The parameters will be listed by treatment group (Placebo, Dose level 1, Dose level 2 and Dose level 3), patient and visit and summarised using standard descriptive statistics. All abnormal values will be identified in patient data listings. Changes from baseline will be described.

PD Analyses: Pharmacodynamic data will be listed by treatment, patient, and visit/time. Summary statistics will be provided by treatment and visit/time. Geometric means and CV will be presented for the primary and secondary PD endpoints.

PD endpoints will be compared between treatments with an ANOVA on logs. Each MOTREM dose group will be compared to placebo with a contract t-test at the 2-sided 10% level.

PK Analyses: Observed MOTREM serum concentrations will be summarised by treatment and corresponding time when sampling occurred. Derived PK parameters will be summarised by treatment.

Clinical Analyses: Several clinical parameters as the clinical events related to sepsis and its complications, the SOFA score total and each sub-score (respiratory, cardiovascular, hepatic, coagulation, renal and neurological system), the vasopressor use, the mechanical ventilation and intubation will be described by treatment group and visit. Standard descriptive statistics will be used.

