9.6 Patients of Reproductive Potential

Since MOTREM is a peptide derived from an endogenous human protein, adverse effects to unborn offspring is considered unlikely. Since the testing of reproductive toxicity is not yet complete, the most stringent precautions for the inclusion of females of childbearing potential will be applied according to CTG guidance (20) will be applied. All female patients will have a serum pregnancy test performed before enrolment into the study. Since the patients will be hospitalised in an ICU during treatment with IMP, contraceptive measures and additional pregnancy tests are not considered required. Since the half-life of MOTREM is very short (approx. 2 minutes), pregnancy testing beyond the stay in the ICU is not considered required.

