11.3.4 End of Study / Premature withdrawal

An End of Study visit will be performed at 28 ± 2 days after the initiation of MOTREM treatment.

The following assessments will be performed:

- Concomitant therapy
- Weight
- SOFA score
- Vital signs
- ECG
- Vasopressor use
- Invasive mechanical ventilation
- Intubation
- Adverse events
- Blood sample for ABG and P/F
- Mortality
- Serious adverse events
- Blood samples for laboratory tests (according to schedule provided in Table 2)
 - Clinical Laboratory

- Anti-drug antibodies (ADA)
- Biomarkers
- RNA profile
- Direct antibody test (direct Coombs)

In case the patient was discharged already, effort should be made to perform as many assessments as reasonably possible. The reasons for missing values must be documented.

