12.11 Study Drug Infusion

The beginning and end of study of each drug infusion will be documented in the eCRF.

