13.4 Period of Observation

Adverse events (serious and non-serious) will be recorded and reported to the sponsor from the time of written informed consent to the end of study (Day 28).

Relevant changes to patient's status will be recorded until day 90.

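### The treatment-emergent window has no end and no split by infusion period, so acute reactions to an infusion of at most 5 days are diluted in tables running to about Day 28

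*Combined protocol and SAP*

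**What the plan says.** Safety is the primary endpoint: "Safety and tolerability will be the primary endpoint and it will be monitored during the course of the study as specified below" (Section 15.1.3). Section 15.1.5 classifies treatment-emergent events by system organ class, preferred term and treatment group. Its definition, "Treatment emergent adverse events (events start after the first dose of investigational treatment", has a second limb for earlier events that "worsened during the study (increased in severity". Neither limb has an end date.

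The end has to be inferred. Section 13.4 records events "from the time of written informed consent to the end of study (Day 28"), and Section 11.3.4 adds that "An End of Study visit will be performed at 28 ± 2 days after the initiation of MOTREM treatment". Section 15.1.3 is looser: "Adverse events: from screening until study completion", in a study with follow-up to Day 90.

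Exposure is much shorter. Sections 8.1 and 11.3.3 stop the infusion 12 (± 2) hours after vasopressor withdrawal, or at 120 (± 2) hours at the latest. Section 9.6 says "Since the half-life of MOTREM is very short (approx. 2 minutes").

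Section 15.1.5 also plans separate summaries of related events, deaths, serious events, events leading to discontinuation and events of interest. None is by onset relative to the infusion. The dates needed for that are collected: event onset in Section 13.3 and infusion times in Section 12.11 ("The beginning and end of study of each drug infusion will be documented in the eCRF").

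**The concern.** Section 6.4.2 names acute and hyper-acute reactions and infusion-site reactions among the risks, and says that there is no experience of the drug in septic shock. Those reactions belong to the infusion and the time just after it. In the planned tables, an event in the first hour and an event on Day 25, at least 20 days after exposure ended, count alike.

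Intensive-care patients have many events in four weeks whichever arm they are in. With 12 per group, that common background pulls the ratio of active to placebo towards one and adds noise. For a safety endpoint, this makes a reassuring table easier to obtain. The protocol already ties another record to the end of infusion: Section 10.7 records concomitant medication until 3 days after it. The event tables have no such link.

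**Working it through.** **The plan's own figures.** Each active dose has 3 (Stage 1) + 9 (Stage 2) = 12 patients. Placebo has 3 × 1 + 9 = 12. The total is 48, as in Section 15.2. The documents state no event rate and no power.

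**Share of the window on drug**, as infusion time divided by 28 days (672 h):
- 120 h: 120/672 = 17.9%, so 82.1% lies after infusion. A visit at Day 26 or Day 30 gives 5/26 = 19.2% or 5/30 = 16.7%.
- 3 days: 3/28 = 10.7%. 2 days: 2/28 = 7.1%.
- Drug left 20 minutes after stopping: 0.5^(20/2) = 0.1%.

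**Illustration 1, event counts.** Assumptions: 12 v 12, Poisson events at 0.2 per patient-day, 3-day infusion, rate doubled on infusion only. Power is for an exact conditional binomial test at 5%. Section 15.1.1 sets two-sided comparisons, but no test is specified for adverse events.
- On infusion, placebo expects 12 × 3 × 0.2 = 7.2 events and active 14.4.
- After infusion, each arm adds 12 × 25 × 0.2 × f, where f is the later rate as a share of the early rate.

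| Window | Active v placebo | Ratio | Power, one-sided | Power, two-sided |
|---|---|---|---|---|
| On infusion | 14.4 v 7.2 | 2.00 | 39% | 27% |
| 28 days, f = 1 | 74.4 v 67.2 | 1.11 | 13% | 8% |
| 28 days, f = 0.25 | 29.4 v 22.2 | 1.32 | 22% | 14% |
| 28 days, f = 0.10 | 20.4 v 13.2 | 1.55 | 29% | 18% |

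The expected excess is 7.2 events in every row; only the background changes. With 0.1 to 0.3 events per day, 2 to 5 infusion days and f = 1, one-sided power is 11–76% on infusion and 7–31% over 28 days. Two-sided, it is 6–65% and 5–21%.

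**Illustration 2, patients with at least one event.** Assumptions: 5-day infusion, 20% placebo risk by Day 5, hazard ratio 3 on infusion only.
- On infusion: placebo 0.20, active 1 − 0.8³ = 0.49, risk ratio 2.44, difference 0.29.
- Over 28 days, the 23 later days add 23/5 = 4.6 multiples of the 5-day hazard, times f. Placebo risk is 1 − 0.8^(1 + 4.6f) and active risk is 1 − 0.8^(3 + 4.6f).

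| f | Placebo | Active | Risk ratio | Difference | Two-sided Fisher power, 12 v 12 |
|---|---|---|---|---|---|
| On infusion | 0.20 | 0.49 | 2.44 | 0.29 | 0.19 |
| 0.25 | 0.38 | 0.60 | 1.58 | 0.22 | 0.12 |
| 0.5 | 0.52 | 0.69 | 1.33 | 0.17 | 0.07 |
| 1 | 0.71 | 0.82 | 1.14 | 0.10 | 0.03 |

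Pooling 36 active v 12 placebo gives 0.37 on infusion, against 0.23, 0.15 and 0.10. A wider grid used 5%, 10% or 20% risk by Day 5, hazard ratio 3 or 5, infusion of 2 or 5 days, and the same f. The risk ratio fell in every case, from 2.4–4.8 on infusion to 1.07–2.59 over 28 days. Power for 12 v 12 was at most 0.55 and 0.32. For the rarest events (5% by Day 5, hazard ratio 3) it was near zero in both windows.

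**The case against.** A reader might infer that every event is counted and drug reactions are buried. The documents do not support that.
- Related events and events leading to discontinuation have their own summaries, and the latter arise on infusion almost by definition. This stands in part: relatedness is a yes/no judgement (Section 13.1) about a drug new to these patients.
- Blood pressure, heart rate, ECG and laboratory values are taken daily on treatment (Section 11.3.2), summarised by group and visit, and described as changes from baseline. A haemodynamic effect could therefore show there. This stands, but it does not replace a table of reported reactions.
- Sepsis-related events have their own forms (Section 12.9) and are described under the clinical analyses. Section 13.1 expressly exempts them only from serious-event reporting and also asks for all adverse events to be recorded. Whether they enter the treatment-emergent tables is not stated.

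A second tempting inference is that everything after infusion is irrelevant because the half-life is so short. Section 6.4.2 names delayed reactions and autoimmunity, and antibodies are tested at Day 10 and Day 28. Pharmacokinetics alone does not set the risk window of an immune modulator. This stands, and the Day 28 table must stay.

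Third, low power over 28 days might be read as the cause of a missed signal. Section 15.2 describes an exploratory pilot without formal sizing. With 12 per group, power is limited in either window.

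Finally, Section 15 leaves detail to a separate SAP that is not in the text reviewed. It may already contain the split.

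**Conclusion.** The point holds as an omission in the analysis of the primary endpoint. The treatment-emergent window has no stated end and runs in practice to about Day 28. At the nominal limits, at least 82.1% of it lies after the infusion, and Section 15.1.5 plans no table that separates the two periods. For acute and infusion-site reactions, the result is a diluted ratio and lost precision. It is not bias between arms, because the concurrent placebo group carries the same background.

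The window shares follow from the protocol. The ratios and power figures rest on assumed event rates, on a drug effect confined to the infusion, and on tests that the plan does not specify for adverse events. They show the direction and plausible size of the dilution and do not predict this trial. The change is worth making because it is cheap and concerns the primary endpoint. It is not a fatal flaw.

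**What to change.** In Section 15.1.5, or in the SAP:
1. Keep the Day 28 treatment-emergent table and state Day 28 as its end. Reconcile the study-completion wording in Section 15.1.3 with Section 13.4.
2. Beside it, add a table by onset during infusion plus a short fixed lag, versus after. Apply the same rule to placebo. Show patients with events and events per infusion-day.
3. Add one fixed window common to all patients, for example first dose to the end of the maximum infusion period plus the lag. Infusion length depends on response, so the on-infusion rates compare arms conditional on something that treatment may change. The fixed window does not. With a one-day lag it covers 6/28 = 21.4% of the period.
4. State whether sepsis-related clinical events enter these tables.

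The cost is one more set of descriptive tables; no new data are needed. Section 15.4 allows unblinding after the last Day 28 visit, and Section 15.5 refers to an analysis already done. If the data are unblinded, label the split post hoc.

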Cytokine distribution and vital signs over time are analysed by a repeated measures ANOVA (mixed models), if significant followed by the Bonferroni post-hoc test.

Data is tested for normality using Kolmogorov-Smirnov-test

HISTORY OF CHANGES

Changes from version 3.1 of the study protocol, dated 08 January 2018

- Introduction of retrospective data collection and exploratory post-hoc analysis of
 - Additional SOFA score data to replace data treated as missing in the original analysis
 - Duration of ICU stay
- Implementation of non-substantial change on plasma sample use documented on note to file dated 08 October 2018

Study protocol version 4.0 applies to study sites outside of France only

Changes from version 2.1 of the study protocol, dated 31 October 2017

- Addition of an interim analysis (section 15.4)
- Clarification of concomitant medication recording
- Minor corrections and clarifications

Study protocol version 3.0 dated 04 January 2017 applies to study sites outside of France only

Changes from version 1.3 of the study protocol, dated 12 September 2017

- Addition of blood samples for DNA analyses related to the TREM-1 signalling pathway
- Addition of a paragraph detailing the analysis and storage of blood samples
- Blood levels of sTLT-1 will not be analysed
- Name change of IMP management provider implemented
- Rating of Adverse Events updated for consistency with eCRF
- Minor corrections and clarifications

Study protocol version 2.0 dated 31 October 2017 applies to study sites outside of France only

Changes from version 1.2 of the study protocol, dated 29 August 2017

- Minor corrections and clarifications on the timing of blood samples in tables 1 and 2

These changes are **classified as non-substantial** by the sponsor according to the EU Clinical Trials Directive and section 8.2 of this study protocol.

Study protocol version 1.2, dated 29 August 2017 implemented the following changes from version 1.0 of the study protocol, dated 20 February 2017

- Changes requested by the French ANSM for sites in France:
 - Addition of exclusion criterion “APACHE II score <14”
 - Measurements of interferon- γ on days 1, 3, 5 and 28
 - Additional timepoint for the measurement of anti-drug antibodies on day 10
 - Direct antibody test (direct Coombs) at baseline (pre-dose), days 10 and 28
 - Addition of free bilirubin to the biochemistry laboratory parameters
 - Update of SUSAR reporting requirements for France
- Minor corrections and clarifications

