MOTREM PK²	MOTREM circulating levels	Baseline (pre-dose), D1 to D5: daily. EOI PK (if feasible) 15 minutes before EOI and 10 min, 30min and 2h after EOI
Cytokines²	TNF α , IL-6, IL-8, IL-10, CCL2 (MCP-1), IFN γ	Baseline (pre-dose), D1, D3 and D5, FU day 28
Activation of vascular endothelium²	soluble CD62E (E selectin), VEGFR-1, VCAM-1, Ang-1, Ang-2	Baseline (pre-dose), D1, D3 and D5, FU day 28
sTREM-1²	soluble TREM-1	Baseline (pre-dose), D1 to D5: daily, FU day 28
RNA profiles²	whole leukocyte RNA profiles (by arrays)	Baseline (pre-dose), 1h, 6h, 12h D1, D3 and D5, FU day 28
Plasma sample for retention	A plasma sample for future exploratory analyses will be stored (see section 12.12.3)	Baseline (pre-dose), D1
Blood sample for pharmacogenetic analyses^{2,3}	Single Nucleotide Polymorphisms of TREM-1 pathway-related genes.	Baseline, other timepoints are acceptable

EOI: End of infusion of study drug

1: Site; 2: Centralised; third party laboratory provider; 3: optional with separate informed consent

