8.2 Adaptive Design

This study incorporates the use of an adaptive design. Study specific adaptive features and their limits are described in Table 3.

Table 3: Adaptive Protocol Features.

Adaptive study design areas	Features	Limits
Repetition of cohorts	
 Cohorts in stage 1 can be repeated in order to obtain more safety and PK data 	
 Each cohort in stage 1 can be repeated only once The randomisation will follow the originally planned system
Dose levels	
 Dose levels in stage 2 of the study can be dropped or adjusted in accordance with PK, safety and tolerability data collected up to the decision-making point 	
 The maximum dose will not exceed 5.0 mg/kg for the loading dose and 3.0 mg/kg/h for the maintenance dose If a dose level is dropped, the planned number of patients may be reassigned to the remaining dose levels.
Samples and assessments	
 Timing of PK and/or biomarker samples may be adjusted in accordance with evolving data and dosing schedule. Additional or less PK and/or biomarker samples may be taken in accordance with evolving data and dosing schedule. Biomarker measurements may be added or removed in accordance with evolving data and dosing schedule (e.g. mTREM-1) 	
 Minimum: sufficient PK samples according to the respective study objective Study specific maximum blood volume will not be exceeded (see section 12.12.8).
Time Window between onset of shock and initiation of treatment	
 The time window of 24 hours between onset of shock and start of study drug infusion may be shortened for stage 2 in accordance with evolving feasibility data from stage 1 	
 The allowed time window in stage 2 will not be shorter than 12 hours

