15.1 Statistical Methods

15.1.1 General Considerations

The analysis will be computed with SAS Version 9.4 (Copyright© 2013 by SAS Institute Inc., Cary, NC, USA).

Unless otherwise specified, baseline is defined as the last planned assessment prior to first dosing and no subgroup analysis is currently planned.

Missing safety, pharmacodynamic, pharmacokinetic and clinical data will not be replaced and will be treated as missing from summary and statistical analyses.

Unless otherwise specified, all treatment comparisons will be two-sided and significance will be assessed at the 5% level.

All safety, pharmacokinetic, pharmacodynamic and clinical data will be summarised by treatment group (Placebo, Dose level 1, Dose level 2 and Dose level 3), and visit, as appropriate.

Qualitative variables will be presented using the number of patients, the number of missing values, the frequency and the percentage per modality.

Quantitative variables will be reported using the number of patients, the number of missing values, the mean, the standard deviation, the median, the first and the third quartiles, the minimum and the maximum.

Between groups comparisons are calculated using an independent t-test or ANOVA-test for quantitative variables with a parametric distribution, or Mann-Whitney test or Kruskal Wallis-test for variables with a non-parametric distribution.

Data is tested for normality using Kolmogorov-Smirnov-test.

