15.4 Interim Analysis

One unblinded interim analysis of complete 28-Day data is planned, after the end of study visit (D28) is complete for all patients, while the study is still ongoing. Some exploratory biomarker and ADA data may not be included in the interim analysis.

The study will be unblinded after the last subject completes the EOS visit and the interim database is available, including cleaned and locked data up to EOS visit (except possibly some of the biomarkers/ADA results). All parties (sponsor, investigators and subjects) may be unblinded at the time of this interim analysis.

The purpose of this interim analysis is to gather preliminary information in order to trigger possible external business decisions. The study will not be stopped early on the basis of this interim review.

Details for this interim analysis will be specified in the statistical analysis plan (SAP). The SAP will be finalised prior to unblinding.

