15.5 Retrospective Collection of Data and Post-hoc Analysis

For exploratory analyses of nangibotide's efficacy for the treatment of septic shock, additional data will be collected on the following parameters:

- SOFA score: For all surviving patients, SOFA scores will be collected up to day 5. The purpose of this is to replace data that have been treated as missing in the original analysis.
- Duration of ICU stay: This is expected to provide efficacy data on a clinically relevant endpoint.

These data have not been collected in the original eCRF. They will be collected from source data at sites to the extent available.

The analysis of this data will follow the principles of the main analysis and will be further specified in a separate statistical analysis plan. The results will be reported separately.

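### The planned PD comparisons use no pre-dose covariate although every PD marker has a pre-dose sample: valid, but less precise than it could be at 12 per arm

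*Combined protocol and SAP*

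**What the plan says.** Two PD analyses are described, neither with a baseline term.

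- Section 15.1.5: "PD endpoints will be compared between treatments with an ANOVA on logs". Each dose is compared with placebo by a t-test on the contrast at the two-sided 10% level.
- Synopsis, Statistical Methods: "Cytokine distribution and vital signs over time are analysed by a repeated measures ANOVA (mixed models", with Bonferroni post-hoc tests if significant. Section 15.2, by contrast, plans no multiplicity adjustment.

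A baseline is available. Section 15.1.1 says "Unless otherwise specified, baseline is defined as the last planned assessment prior to first dosing". Table 2 in section 8.1 lists a pre-dose sample for every PD marker; the sTREM-1 schedule, for example, is "Baseline (pre-dose), D1 to D5: daily, FU day 28". The sentence on changes from baseline in section 15.1.5 belongs to the safety parameters and is descriptive only.

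Sections 15 and 15.1.3 leave further detail to a separate SAP, and section 15.4 adds "The SAP will be finalised prior to unblinding". That SAP is not among the documents. Covariates are therefore unspecified here, which does not show that they were omitted.

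**The concern.** The dose/PD relationship is a secondary objective (section 7), the trial is meant to inform the design of later studies, and there are only 12 patients per arm with no sample size calculation. Patients in septic shock can be expected to differ widely in biomarker level before dosing. Where the pre-dose value predicts later values, an ANOVA that ignores it leaves that variation in the error term. Intervals for the dose-placebo ratios are then wider than the collected data require.

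This is not a matter of bias or false positives. Chance baseline imbalance is already covered by the standard error of the unadjusted comparison. In a particular trial, though, an imbalance of 0.5 SD moves the unadjusted estimate by correlation × 0.5, which is 0.15, 0.25 or 0.35 SD at correlations 0.3, 0.5 and 0.7. Adjustment removes most of that.

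A smaller point is that cytokines are PD markers and could fall under either model. The text does not say which governs.

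**Working it through.** **Planned size.** From sections 9.1 and 15.3, each active arm has 3 (stage 1) + 9 (stage 2) = 12. Placebo has 3 × 1 + 9 = 12. The total is 4 × 12 = 48, which agrees with section 15.2. The plan gives no PD power or precision figure to reproduce.

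**Inputs.** From the plan: four arms of 12, one contrast against placebo, two-sided 10%. Assumed: correlation ρ between log pre-dose and log post-dose value of 0, 0.3, 0.5 or 0.7; normal log values with equal variance; 80% power and a 0.8 SD difference as reference points. Units are the SD of the log value.

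**Formulas.**

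- Unadjusted: variance of the contrast = 2/12 = 0.1667, with 48 − 4 = 44 degrees of freedom.
- Adjusted for log pre-dose value and stage: variance = (2/12)(1 − ρ²)(1 + 1/41), with 42 degrees of freedom. The factor 1 + 1/41 = 1.024 allows for chance baseline imbalance. Stage adds no imbalance as planned, since 3 of 12 patients in every arm come from stage 1.
- 90% interval half-width = t(0.95, df) × √variance. Unadjusted: 1.680 × √0.1667 = 0.69. At ρ = 0.5 the adjusted variance is 0.1667 × 0.75 × 1.024 = 0.128, and 1.682 × √0.128 = 0.60.
- Power and detectable difference come from the non-central t distribution.
- Equivalent patients per arm = 12 / [(1 − ρ²)(1.024)].

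| Analysis | Detectable difference, 80% power (SD) | Power for 0.8 SD | 90% interval half-width (SD) | Equivalent n per arm |
|---|---|---|---|---|
| Unadjusted | 1.03 | 61% | 0.69 | 12 |
| Adjusted, ρ = 0 | 1.04 | 60% | 0.69 | 11.7 |
| Adjusted, ρ = 0.3 | 1.00 | 64% | 0.66 | 12.9 |
| Adjusted, ρ = 0.5 | 0.90 | 71% | 0.60 | 15.6 |
| Adjusted, ρ = 0.7 | 0.75 | 85% | 0.50 | 23.0 |

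The detectable differences are equal at ρ = 0.159. Below that, adjustment costs at most 0.013 SD.

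**Validity check.** In simulations of 8,000 trials per setting, with treatment, baseline and stage in the adjusted model, type I error was 9.8% to 10.6% for both analyses. Adjusted power for 0.8 SD was 61%, 64%, 71% and 84% at the four correlations, against 61% to 62% unadjusted. A second simulation of 20,000 trials per setting, adjusting for baseline only, gave type I error of 9.7% to 9.9%.

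**Stage.** As planned, every arm has 3/12 from stage 1, so leaving stage out causes no bias. Section 8.2 allows repeats: "Each cohort in stage 1 can be repeated only once".

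- One cohort repeated: that arm has 6/15 from stage 1 and placebo 4/13, a difference of 0.400 − 0.308 = 0.092. An assumed stage shift of 0.5 to 1 SD gives 0.05 to 0.09 SD of bias. The two unrepeated arms differ the other way, 3/12 − 4/13 = −0.058.
- Two cohorts repeated: the unrepeated arm differs by 3/12 − 5/14 = −0.107.
- All three repeated: 6/15 in every arm, and no bias.

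**The case against.** The strongest reply is that nothing here is an error. The test is valid, PD is labelled exploratory, the plan sets no PD power target to miss, and the unseen SAP may name covariates. That is accepted, and it is why the point is minor. It does not answer why a stated method should leave an already collected covariate unused.

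The size of the gain is also open to challenge.

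- The correlation is assumed, so the result runs from a trivial loss to nearly double the effective sample.
- Section 15.1.5 does not say whether the logs are raw values or ratios to baseline. With log ratios the variance is multiplied by 2(1 − ρ). At ρ = 0.7 the detectable difference is then 1.03 × √0.6 = 0.80 SD, and ANCOVA gains only about 0.05 SD. At ρ = 0.3 it is 1.03 × √1.4 = 1.22 SD, worse than raw logs, so ANCOVA gains more.
- If the synopsis mixed model treats the pre-dose visit as a time level, it already uses baseline implicitly. The text does not say.
- Twelve per arm is the planned number before any losses from the PD set (section 15.1.2). Patients who stop infusion early have their end-of-infusion assessments only once (section 11.3.3). With 9 per arm the half-width is 0.80 SD unadjusted and 0.70 SD adjusted at ρ = 0.5, a similar relative gain.
- The PD set does not require a pre-dose value, and missing data are not replaced (section 15.1.1). ANCOVA would drop any patient without one.

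These points qualify the size of the gain without removing it. The cytokine question has a natural reading, with the mixed model for profiles and the ANOVA for single-value endpoints such as AUC; one sentence would settle it. The stage argument is weaker: the shift is hypothetical, and eligibility and regimen are the same in both stages.

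**Conclusion.** The concern holds as a minor point about precision. The planned PD comparisons name no pre-dose covariate, although one is scheduled for every PD marker. At 12 per arm, adjustment would lower the detectable difference from 1.03 SD to 0.90 SD at a correlation of 0.5 and to 0.75 SD at 0.7. It would make almost no difference at 0.3 or below. These figures rest on the assumed correlations, normal log values, raw log values as the comparator, and the full planned sample. Neither the validity of the ANOVA nor the primary safety objective is in question. Confidence is medium because the correlation is unknown and the SAP was not seen.

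**What to change.** State in section 15.1.5 or the SAP, for example:

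> Log-transformed PD endpoints (AUC or a single visit) will be compared by ANCOVA with treatment, log pre-dose value and stage. The same two covariates will enter the repeated-measures mixed model for profiles over time. Results will be given as adjusted geometric mean ratios against placebo with 90% confidence intervals.

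Also say which model governs cytokines, and how patients without a pre-dose value are handled. If the SAP already covers this, a cross-reference is enough.

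This should be settled before unblinding. Section 15.5 says of its added SOFA data: "The purpose of this is to replace data that have been treated as missing in the original analysis". That suggests the main analysis may already have been run. If so, keep the planned analysis and label the ANCOVA a sensitivity analysis.

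The cost is a short text edit and no new samples. ANCOVA uses 2 of 44 residual degrees of freedom, has an expected variance penalty of about 2.4% (1/41), and loses any patient lacking a pre-dose value. The mixed model needs visit terms and a covariance structure, but the synopsis already plans such a model for cytokines. Stage is only a safeguard: it cannot rescue a dropped dose arm or separate dose from calendar time within stage 1.
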